4.0 PATIENT REGISTRATION

4.1 Investigator and Research Associate Registration with CTEP

Food and Drug Administration (FDA) regulations and National Cancer Institute (NCI) policy require all individuals contributing to NCI-sponsored trials to register and renew their registration annually. To register, all individuals must obtain a Cancer Therapy Evaluation Program (CTEP) Identity and Access Management (IAM) account at [REDACTED]. In addition, persons with a registration type of Investigator (IVR), Non-Physician Investigator (NPIVR), or Associate Plus (AP) must complete their annual registration using CTEP's web-based Registration and Credential Repository (RCR) at [REDACTED].

RCR utilizes five person registration types.

- IVR — MD, DO, or international equivalent;
- NPIVR — advanced practice providers (e.g., NP or PA) or graduate level researchers (e.g., PhD);
- AP — clinical site staff (e.g., RN or CRA) with data entry access to CTSU applications such as the Roster Update Management System [RUMS], OPEN, Rave, acting as a primary site contact, or with consenting privileges;
- Associate (A) — other clinical site staff involved in the conduct of NCI-sponsored trials; and
- Associate Basic (AB) — individuals (e.g., pharmaceutical company employees) with limited access to NCI-supported systems.

RCR requires the following registration documents:

Documentation Required	IVR	NPIVR	AP	A	AB
FDA Form 1572	✓	✓			
Financial Disclosure Form	✓	✓	✓		
NCI Biosketch (education, training, employment, license, and certification)	✓	✓	✓		
GCP training	✓	✓	✓		
Agent Shipment Form (if applicable)	✓				
CV (optional)	✓	✓	✓		

An active CTEP-IAM user account and appropriate RCR registration is required to access all CTEP and Cancer Trials Support Unit (CTSU) websites and applications. In addition, IVRs and NPIVRs must list all clinical practice sites and Institutional Review Boards (IRBs) covering their practice sites on the FDA Form 1572 in RCR to allow the following:

- Addition to a site roster;
- Assign the treating, credit, consenting, or drug shipment (IVR only) tasks in OPEN;
- Act as the site-protocol Principal Investigator (PI) on the IRB approval; and
- Assign the Clinical Investigator (CI) role on the Delegation of Tasks Log (DTL).

In addition, all investigators acting as the Site-Protocol PI (investigator listed on the IRB approval), consenting/treating/drug shipment investigator in OPEN, or as the CI on the DTL must be rostered at the enrolling site with a participating organization.

Additional information is located on the CTEP website at [REDACTED] For questions, please contact the RCR Help Desk by email at [REDACTED]

4.2 Cancer Trials Support Unit Registration Procedures

Permission to view and download this protocol and its supporting documents is restricted and is based on person and site roster assignment housed in the CTSU Regulatory Support System (RSS).

This study is supported by the NCI Cancer Trials Support Unit (CTSU).

IRB Approval:

For CTEP and Division of Cancer Prevention (DCP) studies open to the National Clinical Trials Network (NCTN) and NCI Community Oncology Research Program (NCORP) Research Bases after March 1, 2019, all U.S.-based sites must be members of the NCI Central Institutional Review Board (NCI CIRB). In addition, U.S.-based sites must accept the NCI CIRB review to activate new studies at the site after March 1, 2019. Local IRB review will continue to be accepted for studies that are not reviewed by the CIRB, or if the study was previously open at the site under the local IRB. International sites should continue to submit Research Ethics Board (REB) approval to the CTSU Regulatory Office following country-specific regulations.

Sites participating with the NCI CIRB must submit the Study Specific Worksheet for Local Context (SSW) to the CIRB using IRBManager to indicate their intent to open the study locally. The NCI CIRB's approval of the SSW is automatically communicated to the CTSU Regulatory Office, but sites are required to contact the CTSU Regulatory Office at

[REDACTED] to establish site preferences for applying NCI CIRB approvals across their Signatory Network. Site preferences can be set at the network or protocol level. Questions about establishing site preferences can be addressed to the CTSU Regulatory Office by email or calling [REDACTED]

In addition, the Site-Protocol Principal Investigator (PI) (i.e. the investigator on the IRB/REB approval) must meet the following criteria in order for the processing of the IRB/REB approval record to be completed:

- Holds an active CTEP status;
- Rostered at the site on the IRB/REB approval (*applies to US and Canadian sites only*) and on at least one participating roster;
- If using NCI CIRB, rostered on the NCI CIRB Signatory record;
- Includes the IRB number of the IRB providing approval in the Form FDA 1572 in the RCR profile; and
- Holds the appropriate CTEP registration type for the protocol.

Additional Requirements

Additional requirements to obtain an approved site registration status include:

- An active Federal Wide Assurance (FWA) number;

- An active roster affiliation with the Lead Protocol Organization (LPO) or a Participating Organization (PO); and
- Compliance with all protocol-specific requirements (PSRs).

4.2.1 Protocol-Specific Requirements for A231601CD Site Registration

- Institutional Approval Document (see Section 4.3.1)
- Practice Level Data Collection Form – The enrolling affiliate/sub affiliate will complete the NCORP Practice Level Data Collection Form and submit it to the CTSU Regulatory Office using the Regulatory Submission Portal located in the Regulatory section of the CTSU website. The form will collect various attributes about the enrolling affiliate/sub affiliate. All of the questions on the form must be complete and the distribution for the analytic cases question must equal 100%. (See form for directions.) The form must be received and complete for site registration approval in RSS. The Practice Level Data Collection Form requirement is submitted once for participation on all NCORP Cancer Care Delivery (CCDR) trials, but will expire two years after it is received. NCORP sites will need to resubmit the Practice Level Data Form to the CTSU in order to continue to enroll to CCDR trials.

4.2.2 Downloading site registration documents

Download the site registration forms from the protocol-specific page located on the CTSU members' website. Permission to view and download this protocol and its supporting documents is restricted based on person and site roster assignment. To participate, the institution and its associated investigators and staff must be associated with the LPO or a Protocol Organization (PO) on the protocol. One way to search for a protocol is listed below.

- Log in to the CTSU members' website [REDACTED] using your CTEP-IAM username and password;
- Click on *Protocols* in the upper left of the screen
 - Enter the protocol number in the search field at the top of the protocol tree; or
 - Click on the By Lead Organization folder to expand, then select *Alliance*, and protocol number *A231601CD*.
- Click on *Documents*, select *Site Registration*, and download and complete the forms provided.

(Note: For sites under the CIRB, IRB data will load automatically to the CTSU.)

4.2.3 Submitting Regulatory Requirements

Submit required forms and documents to the CTSU Regulatory Office using the Regulatory Submission Portal on the CTSU website.

To access the Regulatory Submission Portal log in to the CTSU members' website, go to the Regulatory section and select Regulatory Submission.

Institutions with patients waiting that are unable to use the Regulatory Submission Portal should alert the CTSU Regulatory Office immediately at [REDACTED] in order to receive further instruction and support.

4.2.4 Checking Site's Registration Status

Site registration status may be verified on the CTSU members' website.

- Click on *Regulatory* at the top of the screen;
- Click on *Site Registration*; and
- Enter the site's 5-character CTEP Institution Code and click on Go.
 - Additional filters are available to sort by Protocol, Registration Status, Protocol Status, and/or IRB Type.

Note: The status shown only reflects institutional compliance with site registration requirements as outlined within the protocol. It does not reflect compliance with protocol requirements for individuals participating on the protocol or the enrolling investigator's status with NCI or their affiliated networks.

4.3 Institutional randomization and arm-specific protocols

4.3.1 Institutional Registration

Institutions that are interested in participating in this study must contact the study Project Manager, [REDACTED] for site approval procedures:

Sites should complete the information required in the Institutional Approval Document posted along with Supplementary materials on the Alliance and CTSU websites, and send it to [REDACTED] at the email address listed above. The document will ask for the following information: Name of the site, CTEP Site Code, CTEP Site Code of Main NCORP and contact information (Full name and email) of site staff who will complete the site/practice survey in Medidata Rave.

To approve the site for participation, the project manager will return this document to the institution with a signature of approval. As soon as the site receives IRB approval, it must submit this Institutional Approval Document to the Alliance Registration Office via fax [REDACTED] or email at [REDACTED]. The registration office will register the site to the study and send confirmation to the site via email within 1 business day, in order to be invited to enter site level data in Medidata Rave. The study will not use OPEN for site/practice enrollment. The contact person listed on the Institutional Approval Document will be sent an invitation to enter site level data in Medidata Rave.

Additionally, the site will also submit this document to the CTSU Regulatory portal (see Section 4.2.3) in order to begin patient enrollment.

4.3.2 Randomization will be stratified by practice type (thoracic, major abdominal, and urologic).

The Alliance Statistics and Data Management Center will randomize surgical practices once an institution is interested and eligible to participate. All participants enrolled at a site will receive the intervention to which the treating institution is randomized.

Institutions will be randomized to one of three intervention arms:

- 1) Usual Care
- 2) OPTI-Surg without coach
- 3) OPTI-Surg with coach

4.3.3 Intervention-specific appendices

In order to maintain institutional blinding with respect to OPTI-Surg interventions, information specific to the OPTI Surg arms is provided separately in Appendices III and X. Following randomization, practices should contact [REDACTED] [REDACTED] [REDACTED] to obtain the appendices specific to the intervention arm to which the practice has been randomized. The OPTI-Surg Toolkit/Manual will also be provided to sites at this time.

4.4 Patient Registration Requirements

Informed consent: The patient must be aware of the neoplastic nature of his/her disease and willingly consent after being informed of the procedure to be followed, the experimental nature of the intervention, alternatives, potential benefits, side-effects, risks, and discomforts. Current human protection committee approval of this protocol and a consent form is required prior to patient consent and registration.

Patient completed booklets: Patient questionnaire booklets are to be ordered prior to the registration of any patients. Patient completed booklets can be ordered by downloading and completing the CTSU supply request form, located on the CTSU Forms webpage under the Resources tab. The form must be submitted via the Regulatory Submission Portal on the CTSU website, located under the Regulatory tab. Samples of the booklets are found in Appendix I, which are to be used for reference and IRB submission only. They are not to be used for patient completion.

4.5 Patient Registration/Randomization Procedures

The Oncology Patient Enrollment Network (OPEN) is a web-based registration system available on a 24/7 basis. OPEN is integrated with CTSU regulatory and roster data and with the LPOs registration/randomization systems or the Theradex Interactive Web Response System (IWRs) for retrieval of patient registration/randomization assignment. OPEN will populate the patient enrollment data in NCI's clinical data management system, Medidata Rave.

Requirements for OPEN access:

- A valid CTEP-IAM account;
- To perform enrollments or request slot reservations: Must be on an LPO roster, ETCTN corresponding roster, or participating organization roster with the role of Registrar. Registrars must hold a minimum of an Associate Plus (AP) registration type;
- If a Delegation of Tasks Log (DTL) is required for the study, the registrars must hold the OPEN Registrar task on the DTL for the site; and
- Have an approved site registration for the protocol prior to patient enrollment.

To assign an Investigator (IVR) or Non-Physician Investigator (NPIVR) as the treating, crediting, consenting, drug shipment (IVR only), or receiving investigator for a patient transfer in OPEN, the IVR or NPIVR must list the IRB number used on the site's IRB approval on their Form FDA 1572 in RCR. If a DTL is required for the study, the IVR or NPIVR must be assigned the appropriate OPEN-related tasks on the DTL.

Prior to accessing OPEN, site staff should verify the following:

- Patient has met all eligibility criteria within the protocol stated timeframes; and
- All patients have signed an appropriate consent form and HIPAA authorization form (if applicable).

Note: The OPEN system will provide the site with a printable confirmation of registration and treatment information. You may print this confirmation for your records.

Access OPEN at [REDACTED] or from the OPEN link on the CTSU members' website. Further instructional information is in the OPEN section of the CTSU website at [REDACTED] For any additional questions, contact the CTSU [REDACTED]

4.6 Stratification (or Grouping) Factors and Treatment Assignments

Site randomization will be stratified by practice type:

- Thoracic vs.
- Major abdominal vs.
- Urologic

Patients will be grouped by site randomized arm:

- Arm 1: Usual Care
- Arm 2: OPTI-Surg without coach
- Arm 3: OPTI-Surg with coach

5.0 STUDY CALENDAR

The pre-study testing intervals are guidelines only. Laboratory and clinical parameters during treatment are to be followed using individual institutional guidelines and the best clinical judgment of the responsible physician. It is expected that patients on this study will be cared for by physicians experienced in the treatment and supportive care of patients on this trial.

Pre-Study Testing Intervals

To be completed \leq 28 DAYS before registration: History and physical.

5.1 Patient-level Study Calendar

[Patient-level study calendars for practices randomized to Arms 2 and 3 are provided are Appendices III and X.]

	Screening	Baseline*	Day of Surgery	8 weeks following surgery	12 weeks following surgery
Collected for all eligible (screened) patients					
Postoperative complications and outcomes				X (1)	X (1)
Adverse Event Assessment			X (1)		
Administered to all consenting patients					
Laboratory Studies					
HgB, WBC, Platelets		X		X***	
Serum creatinine		X		X***	
Serum albumin		X		X***	
Tests & Observations**					
ECOG PS		X		X***	
CHAMPS and EQ-5D Qx		X		X***	

* At initial surgical consultation. Questionnaires may be completed at any time following consent, before or after registration. Additionally, sites may leverage satellite NCORP locations to obtain baseline and 8-week follow-up labs and forms.

** Site staff may contact participants via email, U.S. mail, telephone and/or telehealth to administer and obtain questionnaires and assessments, including the CHAMPS Survey and the ECOG Performance Score.

*** Post surgery visits can be +/- 7 days

1. For the purposes of collecting and reporting adverse events into the Alliance database using Rave “adverse events” are those potentially resulting from intervention occurring between baseline and surgery. “Surgical complications” will be assessed 8 and 12 weeks after surgery using the Clavien-Dindo Classification. All CTEP-AERS events should be reported as outlined in [Section 9.0](#).

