Study population: The target of intervention will be surgical practices. The study will include evaluation of patients, providers, and practice organizational and structural factors. Practices will be randomized to utilize the OPTI-Surg package intervention alone, OPTI-Surg with an implementation coach, or usual care. Eligible practices will be engaged in elective cancer operations that are high risk in older adults. Based on administrative data on operative mortality, the following have been identified as high risk in older adults: Gastrectomy 3-10%; colectomy 1-2%; proctectomy 2%; esophagectomy 6-16%; pancreatectomy 2-10%; hepatectomy 3-7%; nephrectomy 2%; total cystectomy 3%; and lung lobectomy/pneumonectomy 3-9%.¹⁹ Eligible practices will have a high prevalence of patients among whom there is a high risk of frailty and be categorized as either a thoracic, major abdominal, or urologic practice. Prior research has shown that > 50% of patients aged 70+ presenting for major surgery are frail.⁶ Based on this data, patients included in the study will be (a) age \geq 70 years who are presenting for surgical evaluation for (b) one of the noted high risk procedures (listed above). To address the variation in expected functional recovery by procedure type, we plan to stratify randomization by three practice types: (1) thoracic, (2) major abdominal, and (3) urologic. Esophagogastric procedures may be included in either the thoracic or major abdominal surgery categories, depending upon the specialty of the operating surgeon.

Endpoints: This study will incorporate both patient-level and site-level data collection. For patient-level data collection, individual eligible patients will be approached for participation and

will sign a consent form for completion of questionnaires preoperatively—at baseline prior to surgery or optimization intervention—and at 8 weeks after surgery.

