Site staff that have not previously activated their iMedidata/Rave account at the time of initial site registration approval for the study in RSS will receive a separate invitation from iMedidata to activate their account. Account activation instructions are located on the CTSU website in the Data Management section under the Rave resource materials (Medidata Account Activation and Study Invitation Acceptance). Additional information on iMedidata/Rave is available on the CTSU members' website in the Data Management > Rave section at [REDACTED] or by contacting the CTSU Help Desk at [REDACTED]

A Schedule of Forms is available on the Alliance study webpage, within the Case Report Forms section. The Schedule of Forms is also available on the CTSU site within the study-specific Education and Promotion folder, and is named Time & Events.

Patient-completed questionnaire booklets for this study are to be ordered prior to the registration of any patients (see Section 4.4). Samples of questionnaire booklets are available in Appendix I for reference and IRB submission only. They are not to be used for patient completion. Booklets must be given to patients to complete and patients should be instructed to return the booklets to site staff either in person or by mail and site staff will enter patient and caregiver responses into Rave.

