8.0 STUDY INTERVENTION

[Additional information for practices randomized to Arm 2 or Arm 3 can be found in Appendix III and Appendix X, respectively.]

The patient-level intervention will involve identification of eligible patients utilizing medical record review at all participating institutions.

After patient registration to the study, the CHAMPS and EQ-5D-5L questionnaires will be administered. Patients will then proceed to surgery. The follow-up CHAMPS and EQ-5D-5L questionnaires will be administered 8 weeks after surgery.

All eligible patients (including those not consented to the study) will be assessed for surgical complications 8 and 12 weeks after surgery.

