8.3 Patient consent and registration

All eligible patients at all participating practices should then be asked to participate in the questionnaire portion of this study, and if willing, consented.

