8.4 Baseline questionnaire administration and pre-surgical interventions

8.4.1 Baseline questionnaires (all practices)

Following patient consent to the study (before or after registration), patients will be asked to complete the CHAMPS and questionnaire and the EQ-5D-5L.

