12.4.2 Primary analysis

The primary analysis will employ a generalized linear mixed model (with Gaussian link function) with a random practice effect to account for clustering within practice and baseline CHAMPS as a covariate to compare 8-week CHAMPS between the combined OPTI-Surg no-coach and coach arms versus usual care. This analysis will include all eligible elderly patients who undergo major cancer surgery, consent to complete CHAMPS questionnaires, and have baseline and 8-week function measured. In supplemental analysis, we will compare pairwise between arms (coach vs usual care, no-coach vs usual care, and coach vs no-coach) using the same method. Supplemental analyses will include model-based analysis with covariates from patient and practice characteristics which appear to differ among randomization arms.

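### Could the baseline CHAMPS used in the primary model be collected after optimization has already begun?

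*Combined protocol and SAP*

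**What the plan says.** Section 1.5 (Endpoints) sets the timing for consenting patients: questionnaires are completed "at baseline prior to surgery or optimization intervention", and again 8 weeks after surgery.

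The operational sections describe the same step without mentioning optimization:

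- Section 5.1, first footnote: "At initial surgical consultation. Questionnaires may be completed at any time following consent, before or after registration". The second footnote adds that "Site staff may contact participants via email, U.S. mail, telephone and/or telehealth to administer and obtain questionnaires and assessments".
- Section 6.1: "patients should be instructed to return the booklets to site staff either in person or by mail".
- Section 8.0: "After patient registration to the study, the CHAMPS and EQ-5D-5L questionnaires will be administered. Patients will then proceed to surgery".
- Section 8.3, which follows the frailty assessment heading (8.2): "All eligible patients at all participating practices should then be asked to participate in the questionnaire portion of this study".
- Section 8.4.1, headed as applying to all practices: "Following patient consent to the study (before or after registration), patients will be asked to complete" the two instruments.

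Section 11.1 runs the patient-level intervention up to surgery. The primary model in Section 12.4.2 uses "baseline CHAMPS as a covariate to compare 8-week CHAMPS" between the combined OPTI-Surg arms and usual care. For Arms 2 and 3, the patient calendars and the content of the frailty assessment and pre-surgical intervention are in Appendices III and X.

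**The concern.** A form completed at any point between consent and surgery meets the literal wording of Sections 5.1 and 8.4.1. Because optimization also runs until surgery, such a form could describe activity that the programme has already raised. Remote completion and mail return make a delay practicable. Frailty assessment also appears before consent in the order of Section 8.

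Only OPTI-Surg practices deliver optimization, so the error would be one-sided. The baseline covariate would be a post-treatment measurement in some OPTI-Surg patients and a true baseline in every usual-care patient. Adjusting for it would subtract part of the treatment effect and pull the primary estimate toward zero. The baseline balance check in Section 12.4.1 would be affected too. Neither Section 12.4.2 nor 12.4.4 identifies late forms.

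**Working it through.** **1. Can the timing statements be followed together?**

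| Section | Anchor for the baseline form | Compatible with 1.5? |
|---|---|---|
| 1.5 | before surgery and before optimization | states the limit |
| 5.1 footnote | initial consultation; after consent, either side of registration | yes; the latitude can be read as concerning registration |
| 5.1 note 1 | adverse-event window runs from baseline to surgery | yes; baseline opens the intervention period |
| 7.5.1 (usual care) | initial consultation | yes; no optimization in this arm |
| 8.0 | registration, then surgery | yes; silent on optimization |
| 8.4.1, then 8.4.3 | questionnaires listed before the pre-surgical intervention | yes; the order agrees |
| 10.4.2 | before the operation | yes; less specific |
| Appendix I booklet | completed at the clinic visit | yes |

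No row requires or expressly permits a form after optimization has begun. A site that obeys Section 1.5 breaks none of the others. Section 4.3.3 also explains why the main text says little about optimization: arm-specific material is held apart so that institutions stay blinded to it.

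**2. The plan's own figures (Section 12.3).** Inputs: 59% frail, mean screening compliance (60% + 80%)/2 = 70%, SD 18.3, cluster effect 0.005, 11 evaluable patients in each of 30 practices (220 OPTI-Surg, 110 usual care).

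- OPTI-Surg mean: 0.59 × (0.7 × 23 + 0.3 × 8) + 0.41 × (0.7 × 23 + 0.3 × 18) = 10.915 + 8.815 = 19.73.
- Usual-care mean: 0.59 × 8 + 0.41 × 18 = 12.10. Difference 7.63; 7.63/18.3 = 0.417.
- Variance inflation: 1 + (11 − 1) × 0.005 = 1.05.
- Standard error: 18.3 × √[(1/110 + 1/220) × 1.05] = 2.19, so the expected z is 3.48.
- Power is 93.6% with no interim look, and 89.5% when the futility rule (two-sided p ≥ 0.323 at half information) is applied. The stated 90% reproduces. Timing of the baseline form enters none of these figures.

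**3. Bias if some baselines were late.** Let b be the slope of 8-week on baseline CHAMPS, f the share of OPTI-Surg patients with a late form, and r the preoperative rise in their score.

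Bias ≈ b × f × r, toward zero. The documents give none of the three, so b = 0.3 to 0.7 and f = 10 to 30% are assumptions.

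- r = 5 kcal (assumed): 0.3 × 0.1 × 5 = 0.15 up to 0.7 × 0.3 × 5 = 1.05 kcal, or 2% to 14% of 7.63.
- r = 10.9 kcal, the plan's full 8-week gain per screened patient (0.59 × 15 + 0.41 × 5), taken as a ceiling: 0.33 to 2.29 kcal, or 4% to 30%.

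Simulation with 220 and 110 patients, without clustering, agreed with the formula to within 0.13 kcal.

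**4. Power under those cases.** With equal SDs at both times, the residual SD is 18.3 × √(1 − b²): 17.5 at b = 0.3 and 13.1 at b = 0.7. The futility look is included.

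| Case | b = 0.3 | b = 0.7 |
|---|---|---|
| All baselines on time | 92% | 99% |
| 30% late, 5 kcal rise | 89% | 97% |
| 30% late, 10.9 kcal rise | 84% | 88% |

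Only the ceiling row falls clearly below the 90% target.

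**The case for a change.** The strongest counter-argument is that a rule stated once in a background section is weak protection when the calendar and procedures that sites work from say something looser. The footnote's permission is broad, Section 8.4.1 covers the OPTI-Surg practices by its heading, and the order of headings is not a timing rule. The primary analysis also needs both CHAMPS scores, which gives a site a reason to recover a missed baseline late. Less favourable assumptions give larger losses. Keeping the SD at 18.3, with b = 0.5, half the OPTI-Surg forms late and a rise of half of 7.63, the contrast falls to 7.63 × (1 − 0.5 × 0.5 × 0.5) = 6.68 and power to 81%. If every OPTI-Surg form were late, the rise were the full 7.63 and b were 0.7, the contrast would be 2.29 and power 15%.

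Part of this stands. The wording is looser than Section 1.5, and the direction of the bias is right. The step from loose wording to a biased estimate does not stand. It needs intervention practices to disregard Section 1.5, and Appendices III and X to be silent or permissive, which could not be checked. It also needs optimization to start before the form is completed. Frailty screening before consent does not show this, because screening is not optimization. The larger losses come wholly from assumed inputs. The 10.9 kcal ceiling credits a postoperative 8-week gain to a preoperative form whose booklet asks about the past 4 weeks.

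A planned sensitivity analysis on late forms would need an optimization start date for each OPTI-Surg patient. The available text does not show that this date is collected. The analysis would also alter baselines on one side of the comparison only.

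**Conclusion.** No change to the plan follows. The protocol contains the limit, and the general sections leave out a detail without contradicting it. The order of 8.4.1 before 8.4.3 and note 1 in Section 5.1 point the same way. Repeating the limit elsewhere would restate an existing rule and would alter neither sample size, alpha, planned power nor the primary model.

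The bias is zero if Section 1.5 is followed. Otherwise, under the assumed 10 to 30% late and slopes of 0.3 to 0.7, it is 0.15 to 1.05 kcal for a 5 kcal rise and at most 2.29 kcal at the ceiling. It would run toward no effect, given that optimization raises activity, so it would not produce a spurious benefit. If the data hold both the questionnaire date and an optimization start date, analysts can count late baselines descriptively without amending anything.

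The conclusion rests on Section 1.5 being applied in the OPTI-Surg practices. It would need another look if Appendix III or X expressly allowed the form after optimization had started.
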